## 4.0 Study Procedures

[figure not shown]
This study is part of a larger EMPOWER QUERI project focusing on innovation in care for women Veterans at VA. Project stakeholders include staff and leadership as subjects and/or key informants. Products include development of an innovative approach for addressing implementation of a care model that addresses anxiety and depression for woman Veterans.

### 5.1 Study Design

EMPOWER QUERI Conceptual Framework. This QUERI Program focuses on strengthening WH organizational capacity for innovation in patient-centered care, using an Implementation Core and three projects as a collective platform for examining how particular characteristics of care models contribute to providers' ability to utilize the models and to patients' engagement and retention in the models. As depicted in our conceptual framework (Fig. 2), the Implementation Core forms the backbone of our program, and relies on an evidence-based implementation strategy, Replicating Effective Programs (REP), and emphasizes multilevel stakeholder engagement and complexity theory. The Core will examine organizational capacity for innovation in the context of local WH care arrangements, which we know to be quite diverse, as well as implementation constructs such as climate and leadership, and novel constructs such as organizational readiness for patient engagement and implementation citizenship. Knowledge of organizational capacity will inform implementation of innovative care models that address anxiety and depression. Implementation outcomes will contribute to development of Implementation Playbooks—brief, user-friendly summations of implementation targets, processes, outcomes, and recommendations for scale-up and spread. Together, these activities will contribute to our ultimate goal of enriching VHA's organizational capacity to engage and retain women Veterans in patient-centered, proactive, personalized evidence-based care.

**Replicating Effective Programs (REP) framework\***  
 featuring *multilevel stakeholder engagement* and the Tool for Evaluation Research Implementation Challenges (TECH)

**EMPOWER QUERI Implementation Strategy: Replicating Effective Programs (REP).** We will use REP across all projects to maximize the implementation science knowledge that will be generated by a common approach. Grounded in theories of Diffusion of Innovation and Social Learning, REP was selected because of its strong evidence base and application in VHA health services research. It also provides a phased *framework* for implementation, with different discrete implementation strategies being employed in different phases. REP's demonstrated effectiveness in promoting uptake of evidence-based practices allows us to focus on its application in varied settings and care models. Use across all projects will allow for further testing and expansion of the framework, particularly through our emphasis on multilevel stakeholder engagement and incorporation of complexity theory. The REP framework consists of four phases (Fig. 3): pre-conditions, pre-implementation, implementation, and maintenance/evolution. Careful attention is paid to intervention packaging during pre- conditions and pre- implementation; training, technical assistance, and fidelity assessment during implementation; and recustomizing during maintenance/evolution.

During each phase, local context is paramount, with varying deployment of the intervention depending on local priorities, needs, and resources. One of our implementation science goals will be to track the relative importance of each discrete strategy in each phase at each site and across sites, as well as in each project and across projects, to inform user-friendly, implementation practice "playbooks" for our partners.

**Enhancing REP with Multilevel Stakeholder Engagement and Complexity Theory.** REP was originally designed to guide dissemination of evidence-based practices in community-based organizations. Kilbourne and colleagues note that "it was not designed to address multilevel barriers to implementation," so they enhanced REP with facilitation, using implementation experts as external facilitators to provide guidance for overcoming implementation barriers. Interestingly, outcomes were favorable for enhanced REP for their primary implementation outcome of uptake (i.e., completed contacts with Veterans with serious mental illness who had been lost to care), but not for increased

utilization of services by patients who had dropped out of care. This prompted us to consider alternate REP enhancements that are 1) more focused on participatory action within complex adaptive systems in VHA WH clinical settings, and 2) potentially more effective in increasing patient engagement. Accordingly, we draw on complexity theory and multilevel stakeholder engagement (Fig. 3). Complexity theory postulates that outcomes in complex adaptive systems are nonlinear and unpredictable; it is a highly relational theory, examining how multiple agents involved in implementation interact in complex ways and “make sense” of implementation in different ways. This emphasis on incorporating multiple perspectives and differing priorities is consistent with our VHA WH roadmap to delivering gender-sensitive comprehensive care for women Veterans, which suggests that multilevel stakeholder engagement is key to improving women Veterans’ health care.

We will operationalize complexity theory through use of the Tool for Evaluating Research Implementation Challenges (TECH) which was designed to systematically assess impacts of implementation challenges and guide potential solutions. Simpson and colleagues recommend this tool under three pre-conditions: 1) “implementation adaptations are expected due to the emergent nature of complex research settings;” 2) the research environment needs to encourage “spontaneous emergent solutions” and creativity; and 3) all research team members must be empowered to participate. Our approach, where all stakeholders are integral to achieving the impact goal, supports these pre-conditions.

TECH, which has been used successfully in VHA and community studies, is codified into a series of interactive steps: identifying challenges (e.g., through observing day-to-day dynamics, listening to complaints, asking questions, etc.), interpreting the challenges in weekly meetings, generating and testing solution strategies, and, if necessary, addressing regulatory issues. Solution strategies are developed through open dialogue among the team members as well as others who might have perspectives on potential solutions. Although applicable to many different types of research, TECH is especially useful for research in complex adaptive systems as a tool for addressing unexpected challenges in systematic and collaborative ways.

Multilevel Stakeholder Engagement in the EMPOWER QUERI. Our QUERI capitalizes on our seasoned team of implementation scientists, health services researchers, and clinicians, supported by a stellar Strategic Advisory Group. Furthermore, we have the distinct advantage of being buttressed by the VHA HSR&D Women’s Health Research Network (WHRN), which is comprised of the Women’s Health Research Consortium and the Women’s Health Practice-Based Research Network (PBRN; §3.3.1), and a research aim on multilevel stakeholder engagement. Our entire team is associated with the WHRN (with EMPOWER QUERI PI [name] also being one of the WHRN PIs). In fact, this QUERI was developed with consistent input from the PBRN Site Leads (some of whom are on our team: [name] (PI), [name], [name]), and the projects will all be conducted at PBRN sites ([name] LoS). Moreover, our QUERI proposal has been strengthened from its inception by invaluable input of women Veterans themselves. Specifically, a newly forming Women Veteran Patient Advisory Council has agreed to serve as an implementation partner for this QUERI Program

([name] LoS); [name] will serve as an advisor to the Council and will use principles of patient engagement in research to guide collaboration and involvement of the Council.

### EMPOWER QUERI Methods

Setting: Women's Health Practice-Based Research Network (PBRN). The PBRN provides a research infrastructure for investigators seeking to increase inclusion of women in VHA research or conduct multi-site women's focused research in VHA. Comprised of 37 VAMCs that see one-third of women Veteran VHA users, the PBRN helps investigators overcome the challenges of multi-site studies through engagement of Site Leads with established working relationships with local clinicians and facility leadership. Site Leads have received implementation training, and have developed across-site relationships through regular national calls and technical support organized by the PBRN Coordinating Center in Palo Alto ([name] LoS).

Modified Stepped Wedge Study Design for Implementation Trials. We will use stepped wedge designs, which rely on sequential roll-out to participating sites over time, while using other sites as controls until they begin implementation. Consistent with our substantial prior experience using these designs in VHA and armed with complexity theory's recognition of nonlinearity of implementation, we will use *modified* stepped wedges (rather than randomized) given their suitability for studying implementation. This design acknowledges that sites are heterogeneous, face multiple constraints, and, as a result, are ready to adopt interventions at different rates. The modified design explicitly considers the timing of implementation spread and addresses the statistical issues introduced by lack of randomization in implementation starts and processes. We will analytically compensate for the design by collecting patient-, provider-, and site-level data that may be associated with timing of the adoption of each intervention.

We will include three levels in our hierarchical stepped wedge models: (1) patient,(2) time of intervention (i.e., when a provider starts using the intervention), and (3) site. Outcomes of interest are measured for all patients at each site within the given intervention time period. We will include four PBRN sites in each of our two implementation trials

Data collection will occur in each of the REP phases (e.g., pre-conditions for 6 months, pre-implementation for 6 months, implementation for 15 months, and maintenance/evolution for 4 months). Similar to previous modified stepped wedge studies, implementation initiates with PCPs. Figure 4 depicts Site A initiating at Quarter 3, Site B at Quarter 4, and so on, with three PCPs at each site, each quarter, for a total of 81 PCPs. The PCPs "turn on" (i.e., use the template in the CV project; refer to the care manager in the CCWV project) as they switch from pre-implementation to implementation.

Modified stepped wedge designs make efficient use of all data available for within-site and between-site comparisons. For the within-site comparison, sites act as their own controls in an evaluation that compares sites pre- versus post-implementation. The comparison examines sites as they cross-over from control to intervention states. The between-site comparison evaluates the intervention period for a site vs. all other intervention and control periods for all sites. By having these two types of

comparison, the design improves on the validity of the evaluation of the intervention, by accounting for historical time trends that may occur outside of the intervention and for site contextual characteristics that may affect site performance.

We will use a modified stepped wedge design to evaluate the implementation in four VA Women's PBRN sites ([name] LoS). In the context of the modified stepped wedge design, the intervention is "turned on" when a PCP at a site makes her/his first referral to the CCWV care manager (see below).

In Year 1, we will begin the REP pre-conditions phase in one VA Women's PBRN sites. We will continue through the phases over the course of four years, with a 15-month implementation phase in order to ensure adequate time to evaluate implementation and sufficient numbers of Women Veterans being exposed to CCWV. Three additional PBRN sites will be "stepped in" during Year 2 at appropriate intervals over time. According to the REP framework and complexity theory, all sites will be encouraged to adapt and tailor set-up and delivery of CALM according to their local resources and care configurations.

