## **5.2 Recruitment Methods**

This study involves both Veteran **Patients** (n=260; 65/site) and VA **Staff** participants (n=60; ~15/site).

**Patients.** Patient subjects will be recruited after making contact with the CCWV care manager via referral from their provider or other staff. The care manager will introduce the research study, and if the person wishes to find out more about the study and possibly participate, the care manager will introduce the Veteran to the RA (if available), ask the Veteran to complete the Research Candidate contact form, add research staff as an additional signer on their CPRS note to automatically notify research staff of interested individuals, or contact the RA through another secure HIPAA-compliant route such as phone call or encrypted email to relay the Veteran's referral information. . The RA will check in with the care manager frequently to learn when women Veterans have been referred, as well as respond to notifications from the CPRS system, phone calls, and encrypted emails. Using a visit-based sampling method, patients are eligible during their first or second visit with the care manager during the 15-month implementation period. The patient will be informed about the details of research participation and asked if they would like to participate in the project. If they agree, the written or verbal (if by phone) informed consent process will be conducted. Patients that are past the enrollment window (i.e., 1st or 2nd visit with care manager), or otherwise unable or unwilling to participate in surveys are still eligible to complete qualitative interviews.

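### The plan says its two stepped-wedge comparisons account for historical time trends, but no stated analysis contains a calendar-period term

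*Combined protocol and SAP*

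**What the plan says.** The roll-out is staged across four sites and is not randomized. Section 5.1 (EMPOWER QUERI Methods) describes the design as "while using other sites as controls until they begin implementation". It then sets out two comparisons:

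- Within site: "sites act as their own controls in an evaluation that compares sites pre- versus post-implementation".
- Between sites: "The between-site comparison evaluates the intervention period for a site vs. all other intervention and control periods for all sites".

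Having both is said to improve validity by "accounting for historical time trends that may occur outside of the intervention".

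After the patient level, the model levels are given as "2) time of intervention (i.e., when a provider starts using the intervention), and (3) site". Non-random timing is to be handled by collecting patient, provider and site data related to when adoption happens. In 5.6, the Quantitative Analysis models referral rates with organization, provider and patient covariates. The impact-focused evaluation adjusts six-month change for patient, provider and site characteristics. The Power Analysis again makes the timing of PCP referrals the second level.

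On whose data enter, 5.1 says "Outcomes of interest are measured for all patients at each site within the given intervention time period". Under 5.2, "patients are eligible during their first or second visit with the care manager during the 15-month implementation period". Section 5.5 adds a utilization history obtained when implementation ends, and Access, Storage and Handling of Secondary Data (under 6.0) limits record extraction to consented, enrolled patients.

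**The concern.** Each PCP's treated quarters all follow that PCP's own untreated quarters. A change over calendar time in staffing, policy or demand therefore moves in step with the intervention, and a pre/post comparison cannot separate the two. A stepped wedge separates them only by comparing treated and untreated units in the same calendar period, which needs a period term or explicit matching on period. The plan states neither. A provider's start date is exposure timing, not the quarter in which an outcome is observed. Covariates that predict early or late adoption do not stand in for it either.

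The between-site sentence does not fill the gap. It pools other periods whatever their calendar time. As a direct contrast it counts already-treated periods as comparators, which conflicts with the same section's statement that other sites are controls until they begin.

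A reader of 5.1 would believe that secular trends are handled. For any outcome compared across turn-on, they would not be.

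**Working it through.** **What can be reproduced.** The plan gives no trend size and no precision figure for this comparison. Its one power figure, 9 PCPs per site (5.6), is not at issue here. The PCP count needed for a layout does not reconcile. Section 5.1 gives "three PCPs at each site, each quarter, for a total of 81 PCPs", whereas three per quarter over five quarters at four sites is 3 × 5 × 4 = 60, and the power minimum gives 9 × 4 = 36. Section 5.1 covers two trials, so 81 may not be a count for this one. Figure 4 is not shown.

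**Assumed layouts.** Site starts at quarters {3,4,5,6}, {3,5,6,7} or {5,6,7,8}. The first extends the stated starts of Q3 for Site A and Q4 for Site B. Observation runs from Q1 to the end of each site's five-quarter (15-month) window. Either 9 PCPs per site (three per quarter for three quarters), 15 per site (three per quarter for five), or the whole site switches at once. Data are assumed for every PCP-quarter, which 5.2 and the extraction rule do not yet provide. PCP models use a random intercept with intraclass correlation 0.01 to 0.20 and 1 or 5 women per PCP-quarter.

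**Step 1: one case by hand.** Whole sites switch, starts Q3 to Q6, true effect zero, outcome rising 1 point per quarter. A site starting at quarter s has mean quarter s/2 before and s + 2 after, a difference of s/2 + 2. Its weight in a model with site effects only is (s − 1) × 5/(s + 4).

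| Start | Difference | Weight | Product |
|---|---|---|---|
| Q3 | 3.5 | 1.429 | 5.0 |
| Q4 | 4.0 | 1.875 | 7.5 |
| Q5 | 4.5 | 2.222 | 10.0 |
| Q6 | 5.0 | 2.500 | 12.5 |
| Sum | | 8.026 | 35.0 |

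False effect = 35.0/8.026 = 4.36 points, that is, 4.36 quarters of trend.

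**Step 2: all layouts.** The loading is the turn-on coefficient when the outcome equals the quarter number, from generalized least squares with site effects. The last column compares standard errors with and without quarter effects.

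| Layout | Loading, no quarter effects | Loading, quarter effects | SE ratio |
|---|---|---|---|
| 9 PCPs per site | 4.17–5.28 | 0 | 1.82–2.02 |
| 15 PCPs per site | 3.81–5.25 | 0 | 1.48–1.64 |
| Whole site switches | 4.36–5.31 | 0 | 2.07–2.29 |

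An assumed trend of 0.5 point per quarter would add 0.5 × 3.81 = 1.9 to 0.5 × 5.31 = 2.7 points. The variance ratio runs from 1.48² = 2.2 to 2.29² = 5.2.

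**Step 3: the between-site sentence as a direct contrast.** With whole-site switching and starts Q3 to Q6 there are 34 site-quarters: 20 treated and 14 not. Removing one site's 5 treated quarters leaves 29, of which 15 (52%) are treated. With no trend at all, a true 10-point effect would appear as 10 × (1 − 15/29) = 4.8 points. Over the other schedules tried, including following all sites to a common end, it is 4.2 to 5.9.

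**Step 4: treated cells with no untreated cell in the same quarter.**

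- 9 PCPs per site, starts Q3 to Q6: Q8 to Q10 give 27 + 18 + 9 = 54 of 144 (37.5%).
- 15 per site: Q10 only, 15 of 180 (8.3%).
- Whole-site switching: 14 of 20 for starts Q3–Q6 or Q5–Q8, and 13 of 20 for {3,5,6,7} (65–70%).

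The two PCP-level counts are the same for all three start patterns.

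**The case against.** The strongest reply is that no stated analysis is shown to be biased. Section 5.6 ties the stepped-wedge model only to referral and retention. Mental health service use appears in 5.5 as a data source, not as an outcome compared across turn-on. That stands, and it means the loadings describe a model the plan leaves open. It does not rescue the claim in 5.1, which no specified analysis supports.

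Several stronger readings are tempting and should be resisted.

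- A reader might infer that the within-site comparison is wholly unadjusted. Sections 5.1 and 5.6 commit to covariates; what is missing is a period term.
- A reader might infer that treated periods must be excluded. They contribute legitimately once period effects are in the model, and the sentence follows a remark about using all available data, so it may mean pooling. Without a period term, that defence is not available as written.
- A reader might infer that referral cannot be affected because it is zero before turn-on. That is true of a PCP's own referrals. The Procedures text under REP Implementation Phases also admits other referring providers and care-manager case finding, so a woman could reach the care manager before her own PCP turns on.
- A reader might infer that there are no pre-turn-on data at all. The utilization history in 5.5 could reach back for enrolled women, but it covers only women later seen by the care manager.

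**Conclusion.** The concern holds as an unsupported design claim and a specification gap. Section 5.1 asserts control of historical trends; neither comparison as worded, nor any model in 5.1 or 5.6, includes calendar period. The textual point needs no assumption.

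The size does. About 3.8 to 5.3 quarters of a trend shared by all sites would load onto the effect without quarter effects, and none with them, under assumed start dates, PCP numbers and complete PCP-quarter data. The trend itself is unknown.

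A reader might infer that the trial's main result is biased by that amount. The documents do not support this: they do not say which outcomes beyond referral and retention are compared across turn-on, and clinical outcomes are stated to be secondary (Veteran Involvement and Characteristics). The correction should be made, but it does not overturn the referral analysis.

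**What to change.** In 5.6, for every outcome compared before and after turn-on, specify fixed effects for calendar quarter and site, a PCP random intercept and a time-varying PCP turn-on indicator. Name those outcomes and state where their pre-turn-on data come from. This means reconciling the all-patients statement in 5.1, the utilization history in 5.5 and the extraction limited to enrolled patients under 6.0. Note that history for enrolled women represents only those later seen by the care manager, a selection that quarter effects do not remove.

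In 5.1, reword the between-site sentence as a calendar-time-adjusted comparison in which not-yet-started periods in the same quarter supply the untreated contrast. Treated periods may stay in the model.

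If this is not done, delete the statement that the comparisons account for historical trends. Deletion costs nothing.

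The full fix has real costs. In the assumed layouts the standard error is about 1.5 to 2.3 times larger (variance about 2.2 to 5.2 times). Quarters from the last turn-on onward have no concurrent control: 8% or 37.5% of treated PCP-quarters with 15 or 9 PCPs per site, and 65–70% of treated site-quarters if whole sites switch. Only a trend shared by all sites is removed; the plan should say so. If records are wanted for women whose PCP is not yet on, the extraction and its approvals must be widened.

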### REP Implementation Phases

**Pre-conditions (Aim 1):** The need for CCWV has been established and the review of effective interventions has been conducted (see above). To ensure that the care model fits local settings and stakeholder priorities, the PI and Co-Investigator [name] will visit the sites and meet with the local team to discuss local structures, care models and processes, educational needs, as well as elements of the proposed CCWV and tailoring options that we have conceptualized (Table 3). Using the TECH, the local team will discuss options for CCWV implementation and anticipated barriers to implementation. Also during this phase, interviews and surveys will be conducted with all consenting key stakeholders, with the exception of patients who will be interviewed and surveyed in the implementation phase (see below).

